### **5.3 METHODS AND TIMING FOR CAPTURING AND ASSESSING SAFETY PARAMETERS**

The Investigator is responsible for ensuring that all AEs (see Section [5.1.1](#) for definition) are recorded on the AE eCRF and reported to the Sponsor in accordance with instructions provided in this section and in Section [5.1](#) and [5.5](#).

For each AE recorded on the AE eCRF, the Investigator will make an assessment of seriousness (Section [5.1.2](#) for seriousness criteria), severity (Section [5.3.3](#)), and causality (Section [5.3.4](#)).

#### **5.3.1 Adverse Event Reporting Period**

Investigators will seek information on AEs at each HV/patient contact. All AE, whether reported by the HV/patient or noted by study personnel, will be recorded in the HV's/patient's medical record. AEs will then be reported on the AE eCRF as follows:

**After informed consent** has been obtained **but prior to initiation of study drug**, only SAEs caused by a protocol-mandated intervention should be reported (e.g., SAE related to invasive procedures such as biopsies). Any other AE should not be reported.

**After initiation of study drug**, all AE, regardless of relationship to study drug, will be reported until the end of follow-up, which is 28 days after the last dose for HVs and 6 weeks after the last dose for patients.

**After the end of follow-up period** (28 days after last dose for HVs and 6 weeks after last dose for patients), investigators should report any deaths, SAE, or other AE of concern that are believed to be related to prior treatment with study drug (see Section 5.5).

### **5.3.2 Eliciting Adverse Event Information**

A consistent methodology of non-directive questioning should be adopted for eliciting AE information at all HV/patient evaluation time-points. Examples of non-directive questions include the following:

“How have you felt since your last clinic visit?”

“Have you had any new or changed health problems since you were last here?”

### **5.3.3 Assessment of Severity of Adverse Events**

Table 1 provides guidance for assessing AE severity.

**Table 1 Adverse Event Severity Grading Scale**

Severity	Description
Mild	Discomfort noticed, but no disruption of normal daily activity
Moderate	Discomfort sufficient to reduce or affect normal daily activity
Severe	Incapacitating with inability to work or to perform normal daily activity

Note: Regardless of severity, some events may also meet seriousness criteria. Refer to definition of a serious adverse event (see Section 5.1.2).

### **5.3.4 Assessment of Causality of Adverse Events**

Investigators should use their knowledge of the HV/patient, the circumstances surrounding the event, and an evaluation of any potential alternative causes to determine whether or not an AE is considered to be related to the study drug, indicating "yes" or "no" accordingly. The following guidance should be taken into consideration:

- Temporal relationship of event onset to the initiation of study drug
- Course of the event, considering especially the effects of dose reduction or discontinuation of study drug
- Known association of the event with the study drug or with similar treatments
- Known association of the event with the disease under study
- Presence of risk factors in the HV/patient or use of concomitant medications known to increase the occurrence of the event
- Presence of non-treatment-related factors that are known to be associated with the occurrence of the event

For patients, causality will be assessed individually for RO7020531 and for NUC analogue(s), if applicable.

### **5.3.5 Procedures for Recording Adverse Events**

Investigators should use correct medical terminology/concepts when recording AEs on the AE eCRF. Avoid colloquialisms and abbreviations.

Only one AE term should be recorded in the event field on the AE eCRF.

For Part 2, Cohort 4, there may be a flu-like symptom specific AE eCRF page, within which each of the symptoms experienced can be captured as well as two allocated eCRF pages for capturing hypotension and hypoxia AEs in case these occur and whether they required medical intervention and management.

#### **5.3.5.1 Diagnosis versus Signs and Symptoms**

A diagnosis (if known) should be recorded on the AE eCRF rather than individual signs and symptoms (e.g., record only liver failure or hepatitis rather than jaundice, asterixis, and elevated transaminases). However, if a constellation of signs and/or symptoms cannot be medically characterized as a single diagnosis or syndrome at the time of reporting, each individual event should be recorded on the AE eCRF. If a diagnosis is subsequently established, all previously reported AEs based on signs and symptoms should be nullified and replaced by one AE report based on the single diagnosis, with a starting date that corresponds to the starting date of the first symptom of the eventual diagnosis.

#### **5.3.5.2 Adverse Events Occurring Secondary to Other Events**

In general, AEs occurring secondary to other events (e.g., cascade events or clinical sequelae) should be identified by their primary cause, with the exception of severe or serious secondary events. However, medically significant AEs occurring secondary to an initiating event that are separated in time should be recorded as independent events on the AE eCRF. For example:

- If vomiting results in mild dehydration with no additional treatment in a healthy adult, only vomiting should be reported on the eCRF.
- If vomiting results in severe dehydration, both events should be reported separately on the eCRF.
- If a severe GI hemorrhage leads to renal failure, both events should be reported separately on the eCRF.
- If dizziness leads to a fall and subsequent fracture, all three events should be reported separately on the eCRF.

All AEs should be recorded separately on the AE eCRF if it is unclear as to whether the events are associated.

### **5.3.5.3 Persistent or Recurrent Adverse Events**

A persistent AE is one that extends continuously, without resolution, between HV/patient evaluation time-points. Such events should only be recorded once on the AE eCRF. The initial severity of the event should be recorded, and the severity should be updated to reflect the most extreme severity any time the event worsens. If the event becomes serious, the AE eCRF should be updated to reflect this.

A recurrent AE is one that resolves between HV/patient evaluation time-points and subsequently recurs. Each recurrence of an AE should be recorded separately on the AE eCRF.

### **5.3.5.4 Abnormal Laboratory Values**

Not every laboratory abnormality qualifies as an AE. A laboratory test result should be reported as an AE if it meets any of the following criteria:

- Accompanied by clinical symptoms
- Results in a change in study treatment (e.g., dosage modification, treatment interruption, or treatment discontinuation)
- Results in a medical intervention (e.g., potassium supplementation for hypokalemia) or a change in concomitant therapy
- Clinically significant in the Investigator's judgment

It is the Investigator's responsibility to review all laboratory findings. Medical and scientific judgment should be exercised in deciding whether an isolated laboratory abnormality should be classified as an AE.

If a clinically significant laboratory abnormality is a sign of a disease or syndrome (e.g., ALP and bilirubin 5 times the ULN associated with cholecystitis), only the diagnosis (i.e., cholecystitis) should be recorded on the AE eCRF.

If a clinically significant laboratory abnormality is not a sign of a disease or syndrome, the abnormality itself should be recorded on the AE eCRF, along with a descriptor indicating if the test result is above or below the normal range (e.g., "elevated potassium", as opposed to "abnormal potassium"). If the laboratory abnormality can be characterized by a precise clinical term per standard definitions, the clinical term should be recorded as the AE. For example, an elevated serum potassium level of 7.0 mEq/L should be recorded as "hyperkalemia".

Observations of the same clinically significant laboratory abnormality from visit to visit should not be repeatedly recorded on the AE eCRF, unless the etiology changes. The initial severity of the event should be recorded, and the severity or seriousness should be updated any time the event worsens.

### **5.3.5.5 Abnormal Vital Sign Values**

Not every vital sign abnormality qualifies as an AE. A vital sign result should be reported as an AE if it meets any of the following criteria:

- Accompanied by clinical symptoms
- Results in a change in study treatment (e.g., dosage modification, treatment interruption, or treatment discontinuation)
- Results in a medical intervention or a change in concomitant therapy
- Clinically significant in the Investigator's judgment

It is the Investigator's responsibility to review all vital sign findings. Medical and scientific judgment should be exercised in deciding whether an isolated vital sign abnormality should be classified as an AE.

If a clinically significant vital sign abnormality is a sign of a disease or syndrome (e.g., high blood pressure), only the diagnosis (i.e., hypertension) should be recorded on the AE eCRF.

Observations of the same clinically significant vital sign abnormality from visit to visit should not be repeatedly recorded on the AE eCRF, unless the etiology changes. The initial severity of the event should be recorded, and the severity or seriousness should be updated any time the event worsens.

### **5.3.5.6 Abnormal Liver Function Tests**

The finding of an elevated ALT or AST ( $>3 \times \text{ULN}$ ) in combination with either an elevated total bilirubin ( $>2 \times \text{ULN}$ ) or clinical jaundice in the absence of cholestasis or other causes of hyperbilirubinemia is considered to be an indicator of potential severe liver injury. Therefore, investigators must report as an AE the occurrence of either of the following:

For Healthy Volunteers and CHB patients in Cohorts 1, 2 and 3:

- Treatment-emergent ALT or AST  $>3 \times \text{ULN}$  in combination with total bilirubin  $>2 \times \text{ULN}$  (of which 35% is direct bilirubin)
- Treatment-emergent ALT or AST  $>3 \times \text{ULN}$  in combination with clinical jaundice

For CHB patients in Cohort 4:

- Treatment-emergent ALT or AST  $>5 \times \text{ULN}$  and  $2 \times$  baseline in combination with total bilirubin  $>2 \times \text{ULN}$  (of which 35% is direct bilirubin)
- Treatment-emergent ALT or AST  $>5 \times \text{ULN}$  in combination with clinical jaundice
- Hepatitis flare, defined as ALT  $>10 \times \text{ULN}$  and  $>2 \times$  baseline level

The most appropriate diagnosis or (if a diagnosis cannot be established) the abnormal laboratory values should be recorded on the AE eCRF (see Section 5.3.5.1) and

reported to the Sponsor immediately (i.e., no more than 24 hours after learning of the event), either as a SAE or a non-serious AE of special interest (see Section 5.3.8).

For the drug discontinuation in patients with abnormal liver function tests, see Section 4.7.1.1.

For Part 2 (CHB patients), documented liver biopsy or Fibroscan® (or equivalent elastography) test results demonstrating chronic HBV infection with absence of cirrhosis and absence of extensive bridging fibrosis (absence of cirrhosis and absence of extensive bridging fibrosis is defined as Metavir <3, recommended cutoff for fibroscan 8.5 kPa) must be available within 6 months prior to randomization. If no results are available, patients must agree to have either a liver biopsy or Fibroscan® (or equivalent) performed during screening.

For liver flares monitoring see Section 5.2.1.

#### **5.3.5.7 Deaths**

All deaths that occur during the protocol-specified AE reporting period (Section 5.3.1), regardless of relationship to study drug, must be recorded on the AE eCRF and immediately reported to the Sponsor (Section 5.4.2). This includes death attributed to progression of chronic HBV infection.

Death should be considered an outcome and not a distinct event. The event or condition that caused or contributed to the fatal outcome should be recorded as the single medical concept on the AE eCRF. Generally, only one such event should be reported. The term “sudden death” should only be used for the occurrence of an abrupt and unexpected death due to presumed cardiac causes in a patient with or without preexisting heart disease, within one hour of the onset of acute symptoms or, in the case of an unwitnessed death, within 24 hours after the patient was last seen alive and stable. If the cause of death is unknown and cannot be ascertained at the time of reporting, “unexplained death” should be recorded on the AE eCRF. If the cause of death later becomes available (e.g., after autopsy), “unexplained death” should be replaced by the established cause of death.

### **5.3.5.8 Preexisting Medical Conditions**

A preexisting medical condition is one that is present at the screening visit for this study. Such conditions should be recorded on the Medical History eCRF.

A preexisting medical condition should be recorded as an AE only if the frequency, severity, or character of the condition worsens during the study. When recording such events on the AE eCRF, it is important to convey the concept that the preexisting condition has changed by including applicable descriptors (e.g., “more frequent headaches”).

### **5.3.5.9 Lack of Efficacy or Worsening of Chronic Hepatitis B Virus Infection**

As this is the first study of RO7020531 in CHB patients (Part 2 only) some of whom are virologically suppressed (Cohorts 1, 2 & 3) and some of whom are treatment naïve (Cohort 4), the effects on viral parameters are being explored as part of the exploratory endpoints in this short study. No functional HBV cure outcome is expected in this study. Lack of RO7020531 efficacy in terms of changes in HBeAg and HBsAg does not qualify for AE in this study.

Medical occurrences or symptoms of deterioration that are anticipated as part of chronic HBV infection should be recorded as AEs if judged by the Investigator to have unexpectedly worsened in severity or frequency or changed in nature at any time during the study. When recording an unanticipated worsening of chronic HBV infection on the AE eCRF, it is important to convey the concept that the condition has changed by including applicable descriptors.

In the event of development of liver decompensation (ascites, varices, Child-Pugh Class B or C clinical classification etc.), this should be reported as an AE and the patient should be discontinued from the study Section 4.7.1.1.

For virological breakthrough, see Section 4.6.1.8 and for liver flares monitoring, see Section 5.2.1. Each of these should be reported as AE.

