## **Part 2: Chronic Hepatitis B Patients**

A follow-up period of 6 weeks will occur for all treatment arms. All patients who complete the 6-week treatment period or discontinue from the study treatment early will be asked to return for follow-up visits at Week 9 and Week 12 and complete assessments as specified in the SoA ([Appendix 1](#)). The visit window for follow-up visits is  $\pm 5$  days.

After the last follow-up visit (Week 12), AEs should be followed as outlined in Section [5.1](#) and [5.5](#).

The last follow-up visit (Week 12) will be reported in eCRF as patient's study completion.

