#### **4.7.1.1 Discontinuation from RO7020531**

HVs/patients have the right to withdraw from the study at any time for any reason.

The Investigators have the right to withdraw HVs/patients from the study in the event of intercurrent illness, AE, pregnancy in female HVs/patients, for administrative or other reasons. The Sponsor should be informed of HVs'/patients' discontinuations from the study or from the study drug.

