## **Part 2: Chronic Hepatitis B Patients**

Individual patients must discontinue RO7020531/placebo if they experience any of the following:

- Safety and tolerability issues, e.g., flu-like symptoms not tolerable and not manageable with symptomatic/*prophylactic* treatment with acetaminophen (*paracetamol*) and/or dose reduction of RO7020531 (*Cohort 4 only*).
- Grade 4 ALT (i.e.,  $\geq 10 \times \text{ULN}$ ) as defined by the Division of Acquired Immunodeficiency Syndrome (AIDS) Table for Grading the Severity of Adult and Pediatric Adverse Events (“DAIDS AE grading table”) ([Appendix 6](#)), confirmed within 48-72 hours.
- Grade 3 ALT (i.e.,  $> 5 \times \text{ULN}$ ) combined with total bilirubin  $> 2 \times \text{ULN}$  (of which  $> 35\%$  is direct bilirubin), or Grade 3 ALT and  $\text{INR} > 1.5$ .
- Grade 4 hematology ( $\text{Hb} < 7.0 \text{ g/dL}$ , absolute neutrophil count  $< 400 /\text{mm}^3$ , absolute lymphocyte count  $< 350/\text{mm}^3$ , or platelets  $< 25,000/\text{mm}^3$ ).
- Any other confirmed (within 48-72h) Grade 3/4 laboratory abnormality deemed clinically significant (based on Investigator’s assessment).
- Development of liver decompensation (ascites, varices, Child-Pugh Class B or C clinical classification).
- Confirmed virological breakthrough after ascertaining that patients are compliant with treatment administration.
- For Cohorts 1, 2 and 3: NUC analogue discontinuation due to safety issues or resistance development.

If 4 or more out of 15 patients (12 receiving RO7020531 and 3 receiving placebo) are discontinued for drug-related safety reasons, enrollment will be halted and safety analysis will be performed. The results of the safety analysis will be provided to IEC/IRB and/or Health Authority, if applicable, before resuming enrollment.

Patients who discontinue study drug before the end of 6-week treatment period:

- Will not resume dosing with RO7020531/placebo. Dosing with NUC analogue in Cohorts 1, 2 and 3 will continue per each patient’s physician discretion and local label.

All prematurely discontinued patients will be asked to come back for an unscheduled visit (see Section 4.6.2.4) to have assessments performed as listed in the SoA (Appendix 1) under “Study Drug Discontinuation / Early Termination”.

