All patients who discontinue the study treatment prematurely should complete the 6-week follow-up period (starting from the date of the last dose taken) as per SoA (Appendix 1). The primary reason for premature study drug discontinuation should be documented on the appropriate eCRF.

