#### **4.7.1.3 Withdrawal from Study**

For withdrawal from the treatment phase in Part 2 see Section 4.7.1.1.

Every effort should be made to obtain information on HVs/patients who withdraw from the study, including withdrawal from the follow-up phase. The primary reason for withdrawal from the study treatment and/or full study (including follow up) should be documented on the appropriate eCRF.

HVs/patients will not be followed for any reason if consent has been withdrawn.

When a HV/patient voluntarily withdraws from the study, or is withdrawn by the Investigator, samples collected until the date of withdrawal will be analyzed, unless HV/patient specifically requests for these to be discarded or local laws require their immediate destruction. A HV’s/patient’s withdrawal from the study does not, by itself, constitute withdrawal of specimens donated to the Research Biosample Repository.

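### Section 5.3.5.9 takes a patient with liver decompensation off the study, but the section it cites stops only study drug and keeps the 6-week follow-up

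*Combined protocol and SAP*

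**What the plan says.** Section 5.3.5.9 deals with worsening of chronic hepatitis B. It makes liver decompensation a reportable adverse event and adds that "the patient should be discontinued from the study Section 4.7.1.1".

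The cited section is headed "4.7.1.1 Discontinuation from RO7020531". Its Part 2 list opens with "Individual patients must discontinue RO7020531/placebo if they experience any of the following", and one entry begins "Development of liver decompensation (ascites, varices, Child-Pugh Class B or C clinical classification". The section then says what happens next. On the visit: "All prematurely discontinued patients will be asked to come back for an unscheduled visit". On follow-up: "All patients who discontinue the study treatment prematurely should complete the 6-week follow-up period", counted from the last dose.

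Two other sections bear on the same patient. Section 5.2.1, under liver flare monitoring, has patients with signs of decompensated disease stop study treatment, and it also cites 4.7.1.1. Section 4.6.2.3 covers patients who complete the treatment period or "discontinue from the study treatment early will be asked to return for follow-up visits at Week 9 and Week 12".

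Withdrawal from the study has its own section, 4.7.1.3, which opens with "For withdrawal from the treatment phase in Part 2 see Section 4.7.1.1".

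**The concern.** Stopping study drug and leaving the study are different acts in this protocol. Section 4.7.1 names them as alternatives. Section 4.7.1.3 has the eCRF record the reason for leaving treatment, the full study, or both. Section 6.3 summarizes completion and discontinuation separately for study treatment and for the entire study. An instruction that names the wrong act can therefore change both what a site does and what it records.

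Two things are at stake. The first is the scheduled follow-up of a patient with a serious hepatic event, in a part of the trial whose primary objective is safety and tolerability (Section 2.1.2). The second is the disposition tables, where a patient recorded as withdrawn from the study would be counted in the wrong category.

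**Working it through.** The plan gives no figure to reproduce. The check is a comparison of instructions, followed by a count of what a literal reading could lose.

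**Instructions for liver decompensation in Part 2**

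| Section | What stops | Follow-up |
|---|---|---|
| 5.3.5.9 | Participation in the study (cites 4.7.1.1) | Not mentioned |
| 4.7.1.1 | RO7020531/placebo | Discontinuation visit, then 6 weeks from last dose |
| 5.2.1 | Study treatment (cites 4.7.1.1) | Extra unscheduled visits for patients with flares |
| 4.6.2.3 | Covers anyone stopping treatment early | Weeks 9 and 12 |

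Only 5.3.5.9 takes the patient off the study. The heading of 4.7.1.1, and the opening line of 4.7.1.3 that sends treatment-phase withdrawal there, show that 4.7.1.1 is the rule for stopping drug.

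**Decompensation after the last dose.** Section 5.2.1 monitors flares for the whole of Part 2, so the event can appear during follow-up. There is then no drug to stop, and the drug-discontinuation visit does not clearly apply. Read literally, 5.3.5.9 could only end the follow-up that remains.

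**Largest loss per patient.** The input is the overview schedule for Cohort 4 in Appendix 1, leaving out the adverse event and concomitant treatment query.

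- Week 9: vital signs; hematology, chemistry and coagulation; urinalysis; PD proteins; whole-blood RNA. That is 5 items, of which the first 3 are safety items.
- Week 12: physical examination; vital signs; ECG; hematology, chemistry and coagulation; urinalysis; pregnancy test; PD proteins; RNA; immunophenotyping; the HBV DNA set; the HBsAg/HBeAg set; the antibody set. That is 12 items, of which the first 6 are safety items.
- All items: 5 + 12 = 17 for a female patient; 17 − 1 = 16 for a male (no pregnancy test).
- Safety items: 3 + 6 = 9 for a female patient; 9 − 1 = 8 for a male.
- PD, immunophenotyping and HBV samples: 17 − 9 = 8.

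**What survives a literal reading.** Section 5.3.1 has adverse events reported until 6 weeks after the last dose. Section 5.4.1 has each event followed until it resolves or is stable. Section 4.7.1.1 asks every prematurely discontinued patient back for one visit. Section 4.7.1.3 asks for every effort to obtain information after withdrawal. The exposure is therefore the scheduled visits and the coding of disposition. Adverse event collection continues.

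**The case against.** The strongest reply is that this is a copy-edit that the cross-reference already cures. The sentence sets out no procedure of its own, and a site that follows the pointer finds the right heading, the decompensation entry and the follow-up rule. Section 4.7.1.1 also opens by giving investigators the right to withdraw a patient from the study for an adverse event, so study withdrawal is not forbidden. The protocol uses the word study loosely elsewhere. Sections 4.6.2.3 and 4.7.1.1 ask Part 1 subjects who leave the study, or the MAD study, early to return for follow-up. Section 6.2 refers to discontinuation from the study where Section 4.7.1 words the same replacement rule in terms of treatment. Finally, the event looks remote: cirrhosis and Metavir 3 or higher are excluded, separate ALT, bilirubin and INR rules stop drug, and Section 5.2.1 reports no abnormal liver laboratory parameters in Cohorts 1 to 3.

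Much of this stands. The intent is clear, and the likely harm is small. It does not make the sentence right. A discretionary right to withdraw is not a direction to do so, and a reader sent to 4.7.1.1 could take 5.3.5.9 as requiring that right to be used. The loose usage in Part 1 comes with an explicit instruction to return; 5.3.5.9 has none. Nor does the cross-reference clearly settle the case where dosing has already ended.

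**Conclusion.** The inconsistency is real and confined to one sentence. Section 5.3.5.9 directs study discontinuation for an event where 4.7.1.1, 5.2.1 and 4.6.2.3 stop treatment and keep follow-up. It is a minor point, worth correcting because it is an operative safety instruction.

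The most that could be lost is two scheduled visits per affected patient (17 items in a female and 16 in a male on the Cohort 4 schedule; 9 and 8 of them safety items), together with a possible misclassification in the disposition summaries. That maximum assumes that decompensation occurs before the Week 9 visit, that the site reads the sentence literally despite the cross-reference, and that no unscheduled assessments take the place of the missed visits. The documents give no rate of decompensation, so no probability is attached. No sample size, endpoint, analysis population or decision rule is affected.

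**What to change.** In Section 5.3.5.9, replace the end of the sentence so that the patient is *discontinued from study treatment, if ongoing, and should complete the 6-week follow-up (see Section 4.7.1.1)*. The words *if ongoing* cover decompensation that appears after the last dose.

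The cost is one clause. No visit, procedure or data item is added, because 4.7.1.1 already calls for the follow-up.
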